11.7.3 Exploratory Variables

11.7.3.1 Retrospective Hypoglycemic Rate

In addition to the analysis of hypoglycemic events from the AE data, a retrospective analysis of the CGM data will be performed to identify hypoglycemic events that may have gone unnoticed by the subject (Table 6, Analysis 1). A retrospective CGM-hypoglycemic event will be defined as anytime the glucose concentration decreases below the threshold of ≤ 3.0 mmol/L. This definition is supported by Seaquist et al (8). Multiple hypoglycemic events while a subject is wearing the CGM device may occur and are defined as having a glucose concentration that returns to > 3.0 mmol/L before decreasing below the threshold again. The number of hypoglycemic events detected between days 2 through 8 of CGM wear for each

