The FreeStyle Libre Pro Flash Monitoring System is approved by the EMA for people 18 years of age or older with diabetes. The FreeStyle Libre Pro Flash Glucose Monitoring System sensor, which requires 12 to 24 hours to calibrate itself after application, will be worn for 8 days and will record the interstitial fluid glucose every 15 minutes. Data from the 2nd through the 8th days of wear will be used for each analysis. The sensor will be blinded to the subject and no subject action will be needed. The subject will also be issued a Mealtime & Insulin Dose Record in which they will record the time of their meals, and insulin use. After 8 days, the subject may remove the sensor, place in the biohazard bag provided and bring it with them to the randomization visit. If the end of the 8-day continuous glucose monitoring (CGM) period coincides with the date of the randomization visit, the sensor can be removed at the visit. Subjects will bring both their Hypoglycemic Events Record and their Mealtime & Insulin Dose Record to the randomization visit.

Subjects who meet the study eligibility criteria will be centrally randomized 1:1 in an open-label fashion to receive either Gan & Lee Insulin Glargine or Lantus® for 26 weeks.

Randomization will be stratified by country. Subjects will continue using their bolus insulin

but will substitute IP for their basal insulin. The Sponsor will ensure that all insulins will be provided to all subjects regardless of medical insurance or reimbursement issues.

At the randomization visit (Visit 2), subjects will receive supply of insulin kits with IP and the Investigator or designee will train subjects on all study procedures and proper dose administration.

Subjects in both treatment groups will be assessed every 2 weeks after Visit 2 (randomization visit) through Week 22 (telephone call); and then at Week 26; they will attend a total of 9 clinic visits (the screening visit, the randomization visit, and at Weeks 2, 4, 8, 12, 16, 20, and 26), 2 brief visits during which a CGM sensor will be applied (8-10 days before the visits at Weeks 12 and 26), and they will be contacted by telephone at Weeks 6, 10, 14, 18, and 22. The Week 26 visit (Visit 9) will be the end-of-treatment visit.

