7.3 Safety

1) American Diabetes Association (ADA) Severe Hypoglycemic AE

A hypoglycemic AE will be classified as "ADA-severe" if the answer to the question "Was third party intervention required for this episode of hypoglycemia?" is Yes on the Hypoglycemia CRF page as mentioned in the ADA hypoglycemia position statement (3).

ADA Severe Hypoglycemic AE should not be confused with hypoglycemia AEs that are graded severe (Grade 3) per National Cancer Institute Common Terminology Criteria for Adverse Events (NCI CTCAE) grade (see Section 11.8.2.1).

2) Adverse Event Leading to Discontinuation of IP

An AE will be classified as an AE leading to discontinuation of IP if the answer to the question "Did the adverse event cause the subject to be discontinued from the study?" is Yes on the AE CRF page.

3) Hypoglycemic AE

An AE will be classified as a hypoglycemic AE if the answer to the question "Is this a hypoglycemic event?" is Yes on the AE CRF page.

4) Injection Site Reactions

Injection site reactions will be identified using the Medical Dictionary for Regulatory Activities (MedDRA) High Level Term = "Injection site reaction".

5) IP-related adverse events

An AE will be classified as related to IP if the relationship to study treatment is Possibly Related, Probably Related, or Definitely Related. Additionally, if the relationship is missing, then the AE will be deemed IP-related.

6) Persistent/Non-persistent Hypoglycemic AE

Hypoglycemic event with Time in hypoglycemia (see definition in Section 7.4) greater or equal to an hour (per CGM) would be classified as persistent. A hypoglycemic event with Time in hypoglycemia below an hour (per CGM) would be classified as non-persistent.

7) Symptomatic Hypoglycemic AE

A Hypoglycemic AE will be classified as symptomatic if the answer to the question "Was subject aware of symptoms?" is Yes on the Hypoglycemia CRF page.

8) Treatment-emergent adverse events

Treatment-emergent adverse event (TEAE) is an event that started or worsened in severity on or after the day of the first dose of IP but not more than 30 days after the subject's last dose of IP.

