7.4 Exploratory

1) Continuous Glucose Monitoring Device Day of Wear

The day of wear will be defined as starting exactly $(x-1)*24$ hours and ending $x*24$ hours after the time of the first assessment at the given visit, where x is the day of wear from 2 to 8 days.

2) Time in hypoglycemia

The time in hypoglycemia will be defined using the CGM data from days 2 through 8 of wear at each of the 3 visits where CGMs are applied as the sum of the time where the glucose value is <3.0 mmol/L.

PPS will be used for some sensitivity analyses (for example, the primary endpoint for immunogenicity [from Section 11.6.1.3] and HbA1c [from Section 11.7.1.3]).

A second Per Protocol Analysis Set (PPS2) will be composed of all subjects whose treatment assignment was randomized, who received at least 1 partial dose and do not have any immunogenicity-interfering important protocol deviations (IIIPD) as defined in Section 11.3 up to visit Week 26. A third Per Protocol Analysis Set (PPS3) will be composed of all subjects whose treatment assignment was randomized, who received at least 1 partial dose and do not have any efficacy-interfering important protocol deviations (EIIPD) as defined in Section 11.3 up to visit Week 26. Subjects in the PPS2 and PPS3 will be grouped according to actual treatment received. The PPS2 and PPS3 are larger and less restrictive analysis sets than the PPS and will be used for some sensitivity analyses for the primary endpoint for immunogenicity [from Section 11.6.1.3] and HbA1c [from Section 11.7.1.3], respectively.

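### A CGM reading of exactly 3.0 mmol/L counts as a hypoglycemic event in SAP 11.7.3.1 but adds no time in hypoglycemia in SAP 7.4, so the two exploratory CGM summaries can disagree

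*SAP*

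**What the plan says.** **Event rate (SAP 11.7.3.1).** An event is "anytime the glucose concentration decreases below the threshold of ≤ 3.0 mmol/L". Repeat events are separated by "having a glucose concentration that returns to > 3.0 mmol/L before decreasing below the threshold again". The visible text gives no minimum duration and no minimum recovery time.

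**Time in hypoglycemia (SAP 7.4, item 2).** This is "the sum of the time where the glucose value is <3.0 mmol/L", calculated "using the CGM data from days 2 through 8 of wear at each of the 3 visits where CGMs are applied".

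**Sampling (Protocol 8.1).** The sensor "will record the interstitial fluid glucose every 15 minutes".

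**Further use of the time definition (SAP 7.3, item 6).** "Hypoglycemic event with Time in hypoglycemia (see definition in Section 7.4) greater or equal to an hour (per CGM) would be classified as persistent". These adverse events are reported in SAP Table 6, Analyses 9 and 10.

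**Status.** The rate and the time measure are listed as separate exploratory endpoints (Protocol 8.7.4, SAP 6.4). They appear side by side as Analyses 1 and 2 in SAP Table 6. Protocol 12.10 says they will be summarized.

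**The concern.** Both measures come from the same sensor readings over the same days, but they disagree about a reading of exactly 3.0 mmol/L. The rate includes it and the time measure excludes it. A subject can therefore appear in the rate table with one or more events and in the time table with zero minutes, purely because of the definitions.

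The entry wording adds to the problem. Falling below a threshold that is itself written as less than or equal to 3.0 can be programmed in two ways.

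A second, separate feature is that recovery can be a single reading. A trace that hovers around the cut-off is then counted as several events.

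What is at stake is the internal consistency and interpretability of two exploratory summaries. The CGM rate is meant to pick up events that subjects did not notice, in an open-label trial where the SAP itself says sites documented hypoglycemia differently. A clear definition is therefore worth having.

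**Working it through.** The documents state no expected CGM rate, time or power, so there is no plan figure to reproduce. The check applies the written rules to short traces.

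**Inputs.**
- Event opens at ≤ 3.0 and ends at > 3.0 mmol/L (SAP 11.7.3.1). The end rule is what places 3.0 inside the event.
- Time counts only at < 3.0 mmol/L (SAP 7.4).
- One reading every 15 minutes (Protocol 8.1). Days 2 to 8 give 7 × 96 = 672 readings per complete wear.
- Assumption: each qualifying reading stands for 15 minutes. The visible SAP text does not say how readings become minutes.

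**Step 1: apply the rules.** Time = 15 × number of qualifying readings. Events = number of separate runs of qualifying readings.

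| Trace (mmol/L) | As written | Both at < 3.0 | Both at ≤ 3.0 |
|---|---|---|---|
| A: 3.1, 3.0, 3.1, 3.0, 3.1 | 2 events, 0 min | 0 events, 0 min | 2 events, 30 min |
| B: 3.4, 2.9, 3.1, 2.9, 3.1, 2.9, 3.2, 3.6, 3.8 | 3 events, 45 min | 3 events, 45 min | 3 events, 45 min |
| C: 3.2, 2.9, 3.0, 2.9, 3.2 | 1 event, 30 min | 2 events, 30 min | 1 event, 45 min |

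Trace A shows the mismatch. Either single cut-off removes it.

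Trace B shows that splitting is a different matter. It gives three events under either cut-off, but one event if recovery must last two consecutive readings.

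Trace C shows that moving to < 3.0 does not only remove events. A lone 3.0 between two lower readings now separates them. The two-reading recovery rule brings C back to one event.

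**Step 2: which cut-off disturbs less.** Take three readings of 2.9 and one of 3.0. Under < 3.0 the time is 3 × 15 = 45 minutes, short of the one hour in SAP 7.3. Under ≤ 3.0 it is 4 × 15 = 60 minutes, which is persistent. Harmonizing at ≤ 3.0 would therefore change a safety classification, and harmonizing at < 3.0 would not. Appendix 2 also starts Grade 2 hypoglycemia strictly below 3.0 mmol/L.

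**Step 3: size of the cut-off effect (illustrative).** Simulated traces used these assumptions: smooth autocorrelated log-normal glucose, mean 8.5, SD 3.0 or 3.5 mmol/L, correlation time 2 or 3 hours, reading noise SD 0 to 0.3 mmol/L, storage to 0.1 mmol/L, and 400 subjects per scenario.
- Events at ≤ 3.0 against < 3.0: about 15% more (2.19/1.90 = 1.15) to 35% more (0.50/0.37 = 1.35) per week of wear.
- Time at ≤ 3.0 against < 3.0: 23% to 36% more.

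These figures depend on resolution. In separate runs with smoother traces the event excess was 19% to 24% at 0.1 mmol/L. It was 11% to 14% on a 1 mg/dL grid divided by 18, where 54/18 = 3.0 exactly. With a divisor of 18.016 and no rounding it is nil: 54/18.016 = 2.997 and 55/18.016 = 3.053, so no reading equals 3.0.

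**Step 4: size of the splitting effect (illustrative).** In the first set of simulations, at the ≤ 3.0 cut-off, ending an event on one reading rather than two gave these excesses:
- No noise: 3% more (0.32/0.31) to 5% more (1.11/1.06).
- Noise SD 0.3 mmol/L: 20% more (2.69/2.24) to 32% more (2.37/1.80).

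**The case against.** The rate and the time measure are separate endpoints, and nothing says they must describe the same episodes. The end rule at > 3.0 shows how a value of 3.0 is to be treated, so the entry wording can be called loose rather than contradictory. The aim is to find unnoticed events, which can favor a sensitive single-reading rule, and the SAP cites a source for its definition that cannot be checked here. The visible text of 11.7.3.1 breaks off mid-sentence and 11.7.3.2 is not available, so a further rule cannot be excluded.

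Much of this stands. It rules out calling the single-reading rule an error. It does not remove the conflict at 3.0, which is explicit in both sections. Any further rule would still have to be squared with the open-ended event definition.

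A reader might infer more than the documents support:
- **That the event rate is inflated.** A minimum-recovery rule can only merge events, so at the same cut-off the written count is never lower. Inflation, however, is measured against a sustained-episode definition that appears nowhere in the documents.
- **That two readings should be required both to open and to close an event.** This is a debatable choice. For 3.0, 3.1, 2.9, 3.1, 3.0, opening on two consecutive readings < 3.0 returns no event at all.
- **That the CGM rate is the only hypoglycemia measure free of open-label reporting.** CGM time in hypoglycemia and central-laboratory fasting glucose (SAP 6.3.2; Table 6, Analyses 2 and 14) are also free of it.
- **That the treatment comparison is biased.** The rule is the same in both arms. The negative binomial comparison (Table 6, Analysis 11) uses hypoglycemic adverse events, not the CGM rate.

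**Conclusion.** The point holds as a minor inconsistency. As written, SAP 11.7.3.1 and SAP 7.4 treat a reading of exactly 3.0 mmol/L in opposite ways, so the plan can report CGM events with zero minutes in hypoglycemia. That follows from the text alone, apart from any rule in the parts of the SAP that are not visible.

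The size is not determined by the documents. It depends on how often readings are stored as exactly 3.0, and hence on sensor noise and resolution. Under the assumptions shown, the cut-off effect on the event count runs from nil to about 35%, and the splitting effect from about 3% to 32%. Neither range should be read as an estimate for this trial.

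The measures are exploratory and summarized. No treatment bias is shown, and the primary and key secondary conclusions are unaffected.

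**What to change.** Use one cut-off for both CGM measures. The choice that leaves SAP 7.4, the persistent-event classification in SAP 7.3 and the Appendix 2 grading unchanged is < 3.0 mmol/L. In 11.7.3.1 an event would then open at a reading < 3.0 and end at a reading ≥ 3.0. State how a reading converts to minutes, and reconcile the wording with the rest of 11.7.3.1 and with 11.7.3.2.

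As an optional sensitivity analysis, also report the count with events merged unless recovery lasts at least two consecutive readings. This shows how far the rate depends on values hovering at the cut-off, without replacing the main definition.

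The cost is SAP wording and a small programming change, with no new data. The downside is that readings of exactly 3.0 no longer open an event, and a single 3.0 between two lower readings now separates two events. The merged count covers the second effect.

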**Table 6: Listing of hypoglycemic event summaries and analyses**

Analysis description	Section Reference	Tables Associated
1. Summary of Retrospective Continuous Glucometer Monitor (CGM): Hypoglycemia Rate	Section 11.7.3.1	Table 14.3.3.4.1
2. Retrospective Analysis of Continuous Glucometer Monitoring (CGM): Time in Hypoglycemia, Hyperglycemia and Euglycemia	Section 11.7.3.2	Table 14.3.3.4.2
3. Overall Summary of Treatment-Emergent Adverse Events	Section 11.8.1	Table 14.3.2.1
4. Treatment-Emergent Adverse Events by System Organ Class, Preferred Term	Section 11.8.1	Table 14.3.2.2
5. Hypoglycemic Treatment-Emergent Adverse Events by System Organ Class, Preferred Term, and Maximum CTCAE Grade (based on lowest blood glucose values measured by test method)	Section 11.8.2.1	Table 14.3.2.6.1
6. Severe Hypoglycemic Treatment-Emergent Adverse Events by Preferred Term	Section 11.8.1	Table 14.3.2.7
7. Serious Hypoglycemic Adverse Events by Preferred Term	Section 11.8.3	Table 14.3.2.13
8. IP-Related Serious Hypoglycemic Adverse Events by Preferred Term	Section 11.8.3	Table 14.3.2.14
9. Summary of Symptomatic or Persistent Hypoglycemic Treatment-Emergent Adverse Events	Section 11.8.2	Table 14.3.2.17
10. Summary of Symptomatic or Persistent Hypoglycemic Treatment-Emergent Adverse Events by Site	Section 11.8.2	Table 14.3.2.18
11. Analysis of Hypoglycemic Treatment-Emergent Adverse Events	Section 11.8.2	Table 14.3.2.19
12. Summary of Reported ADA Hypoglycemic Treatment-Emergent Adverse Events	Section 11.8.2.2	Table 14.3.2.20
13. Overall Summary and Analysis of Treatment-Emergent Adverse Events by ERIPD Subgroup in SS, PPS2, and PPS3	Section 11.8.1	Table 14.3.2.21; 14.3.2.22; 14.3.2.23; 14.3.2.24
14. Maximum Post-baseline Fasting Glucose CTCAE Grade	Section 11.8.4.1	Table 14.3.3.4.16

Subject incidence of the following TEAEs will be tabulated by preferred term in descending order of frequency in the total column:

- CTCAE Grade \geq 3 TEAEs
- Hypoglycemic TEAEs
- CTCAE Grade 3 or Greater Hypoglycemic AEs
- IP-related TEAEs
- CTCAE Grade \geq 3 IP-related TEAEs
- Fatal AEs
- SAEs
- IP-related SAEs
- Serious Hypoglycemic AEs
- IP-related Serious Hypoglycemic AEs
- AEs Pertaining to Injection Site Reactions

A forest plot of the difference in incidence rates and CIs of TEAEs preferred terms with a $\geq 5\%$ difference in incidence between groups will be summarized. The 90% CIs will be computed using Wald method for risk difference without continuity correction.

Additionally, the hypoglycemic event rate will be compared between treatment groups using a negative binomial regression model (Table 6, Analysis 11). The response variable in the model will be the number of hypoglycemia events. The model will include factors for treatment group and site. Site has been included as a factor as different handling of documentation of hypoglycemia event are identified. The logarithm (to base e) of the follow-up time will be used as an offset variable in the model to adjust for subjects having different exposure times. The estimated treatment effect and the corresponding 95% CI, as well as the 2-sided p-value will be presented.

A sample SAS code fragment is provided below for reference:

```
proc genmod data = <data>;
  class trt site;
  model count = trt site / dist = negbin offset = time_log;
  lsmeans trt / ilink diff exp cl;
run;
```

All TEAEs will be listed for subjects in the SS. A listing of all TEAEs leading to discontinuation of IP will be provided.

All non-treatment-emergent AEs recorded on the CRF will be listed separately for all screened subjects.

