### 12.4 Randomization

Subjects will be randomized in a 1:1 ratio to Gan & Lee Insulin Glargine Injection or Lantus® treatment. Subject randomization will be stratified by country.

Registration and randomization will take place using a centralized IXRS. At registration, the IXRS will assign a unique subject identification number that will be used on all of that subject's eCRFs and serious adverse event report forms.

The study is not blinded. However, to avoid the introduction of operational bias into final study results and to increase the interpretability and reliability of the data, certain roles of the Sponsor and study team will be blinded. Details will be provided in the Data Blinding and

Documentation of Aggregate Data Dissemination Plan (hereafter referred to as the Blinding Plan).

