5.1 Sample Size and Power

Enrollment was planned for 550 subjects overall (275 subjects per treatment group). The primary analysis for the immunogenicity primary endpoint was to be an equivalence test for the difference in proportion of subjects who develop treatment-induced AIAAs between Gan & Lee insulin Glargine Injection and Lantus® using the 2 Wald one-sided tests (TOST) with $\alpha=0.05$ (Chow and Shao 2002 (1)). After scientific and regulatory review, the method to evaluate immunogenicity equivalence will be the 90% confidence intervals of risk difference from the logistic regression analysis (see Section 3.1). Under this newly adopted approach, no power loss is expected.

This sample size of 275 subjects per treatment group was chosen to achieve over 80% power using the TOST equivalence test for two proportions, a risk difference of zero and equivalence margins dependent on the observed treatment-induced AIA rate per Table 3 below. For example, a total sample size of 550 will provide approximately 85% power for the TOST equivalence test using a treatment-induced AIA rate of 30% and a margin of 12% (Table 3). The treatment-induced AIA is defined as newly confirmed positive AIA development or important (at least a 4-fold) increase in AIA titers, after baseline and up to visit Week 26 (see the definition of Primary Endpoint in Section 6.1 and Section 7.2). No drop outs are considered in the calculation. A larger than expected early discontinuation rate was observed as part of study monitoring activities and therefore protocol amendment 3 approved on 25-Apr-2019 included procedures to encourage subjects to return for assessments even if they had discontinued treatment early.

The appropriate similarity margin, based on the actual observed event rate for the intended reference product, will be used for final analysis after database lock as summarized in Table 3 below. The power calculation in the table was adapted for a sample size of 550 using the treatment-induced AIA rate for the reference product. Linear interpolation will be used for values between AIA rates in the table.

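### The adverse-event forest plot picks preferred terms by their observed arm difference, so its 90% CIs undercover when the true difference is well below 5 points and uncommon terms are shut out

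*SAP*

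**What the plan says.** The rule is in the SAP's TEAE summaries (Section 11.8.1), in the text after Table 6. The SAP plans "A forest plot of the difference in incidence rates and CIs of TEAEs preferred terms with a" minimum gap between the arms. The plot is limited by the words "preferred terms with a $\geq 5\%$ difference in incidence between groups will be summarized". On the interval, the SAP says "The 90% CIs will be computed using Wald method for risk difference without continuity correction". The text shown gives the plot no incidence threshold and no prespecified list of terms.

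The planned size is in SAP Section 5.1: "Enrollment was planned for 550 subjects overall (275 subjects per treatment group"). Protocol Section 12.4 gives the 1:1 allocation.

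Other outputs cover the same events:
- SAP Table 6, Analysis 4 tabulates TEAEs by system organ class and preferred term.
- The list after Table 6 adds preferred-term tables for, among others, serious, IP-related, hypoglycemic and injection-site events.
- All TEAEs in the safety set are listed.
- The hypoglycemic event rate is compared between arms by negative binomial regression with a 95% CI.

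The Protocol synopsis treats the safety variables as descriptive.

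**The concern.** An interval has its nominal coverage when the reason for showing it does not depend on the result it shows. Here a term appears because its observed difference is large. When the true difference is small, the plotted terms are the ones that chance has pushed outwards, and their intervals are centred too far from the truth.

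The filter is also on an absolute difference, so it treats common and uncommon terms unequally. A common term can pass on noise. An uncommon term can carry a clear imbalance and fail.

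This matters for a biosimilar. Comparing safety with Lantus is a secondary objective, injection-site reactions are a named safety endpoint (Protocol 8.7.3.2), and Protocol Section 6.3 says that hypersensitivity symptoms and injection-site reactions will inform the interpretation of immunogenicity. If such terms occur in fewer than 5% of each arm, which is an assumption, the plot cannot show them.

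**Working it through.** **Inputs.** n = 275 per arm (SAP 5.1). Inclusion if the observed difference is at least 5 percentage points; the SAP does not say absolute or relative, and absolute is assumed. 90% Wald interval without continuity correction, z = 1.645. The documents give no true incidences by term, so the rates below are assumptions shown as a range.

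**Check of n against a stated figure.** The plan states no figure for the plot. Its power example can be reproduced: SE = √(2 × 0.30 × 0.70 / 275) = 0.0391, and power = 2Φ(0.12/0.0391 − 1.645) − 1 = 84.6%, against about 85% stated.

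**Threshold in subjects.** 0.05 × 275 = 13.75, so a term needs a gap of at least 14 subjects (14/275 = 5.09 points). A term observed in fewer than 5% of both arms (13 subjects or fewer in each) can never qualify.

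**Method.** With x₁ ~ Bin(275, p₁) and x₂ ~ Bin(275, p₂), d = (x₁ − x₂)/275 and SE = √[p̂₁(1 − p̂₁)/275 + p̂₂(1 − p̂₂)/275]. All pairs were enumerated. P(plotted) is the total probability of pairs with |x₁ − x₂| ≥ 14. Coverage among plotted terms is the share of that probability in which d ± 1.645 SE contains p₁ − p₂.

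| True rates | P(plotted) | Coverage if plotted | Mean plotted difference |
|---|---|---|---|
| 5% v 5% | 0.8% | 0% | – |
| 10% v 10% | 5.5% | 0% | – |
| 20% v 20% | 15.0% | 33% | – |
| 30% v 30% | 20.9% | 51% | – |
| 13% v 10% | 24.2% | 79% | 6.4 points (true 3) |
| 4% v 1% | 7.8% | 54% | 5.6 points (true 3) |
| 10% v 5% | 51.4% | 91% | 6.7 points (true 5) |
| 25% v 20% | 51.3% | 90% | 7.7 points (true 5) |

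Without selection, coverage in these scenarios is 89% to 90%.

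**Where a plotted interval can include zero.** The lowest observed pooled incidence at which this happens is 16%. At 51 v 37 subjects (88/550 = 16%), d = 5.09, SE = 3.12 and the interval is −0.04 to 10.22. One subject fewer in each arm (50 v 36, 86/550 = 15.6%) gives 0.01 to 10.17. Below 16% observed, every plotted interval excludes zero.

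**Uncommon terms.** At a true 4% v 1%, the 90% interval would exclude zero in 76% of trials, but the term is plotted in 7.8%. At 3% v 1% the figures are 54% and 1.0%. Two observed outcomes side by side:
- 13 v 0 subjects: d = 4.73, SE = 1.28, interval 2.6 to 6.8, Fisher p = 0.0002. Not plotted.
- 69 v 55 subjects: d = 5.09, SE = 3.56, interval −0.8 to 10.9. Plotted.

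**Effect of selecting on pooled incidence.** With an illustrative cut-off of at least 2% in both arms combined, coverage among displayed terms is 89.9% at 5% v 5%, 89.7% at 10% v 10%, 89.9% at 20% v 20%, 90.3% at 5% v 2% and 92.8% at 4% v 1%. A true 4% v 1% term is then shown 81% of the time, with a mean displayed difference of 3.3 points. A cut-off of 2% in either arm is less clean, because for rare terms it still selects partly on imbalance: coverage is 65.5% at 1% v 1%.

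**The case against.** The strongest reply is that nothing is decided on this plot. It has no hypothesis or margin and feeds neither the primary nor the key secondary analysis. Its filter is stated openly, and showing the largest observed imbalances is a recognisable descriptive purpose. That stands, and it limits the weight of the point.

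It is also true that the omitted terms are reported. A 13 v 0 imbalance would appear in the preferred-term table, injection-site reactions have their own table, and the hypoglycemia rate has its own interval. What an uncommon term lacks, in the text shown, is a between-arm interval. A reader with the counts could compute one.

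Three stronger readings are tempting, and the documents do not support them:
- A reader might infer that plotted intervals undercover in general. They do not: when the true difference is about 5 points, coverage is 91.8% (8% v 3%), 90.9% (10% v 5%) and 89.6% (25% v 20%).
- A reader might take the 16% boundary as a true rate below which coverage is always zero. It is an observed pooled rate. With truly equal arms, coverage is 2.9% at 14% and 7.2% at 15%.
- A reader might infer that absence from the plot will be presented as absence of a difference. Nothing in the plan says so.

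Finally, the opening of SAP 11.8.1 is not in the supplied text and the output shells are a separate document. Another term-level interval could be specified there. The selection problem does not depend on that, because it lies in the visible rule.

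**Conclusion.** The concern holds as a weakness of a descriptive display. Selecting on the observed difference makes the plotted intervals undercover when the true difference is well below 5 points, most severely for terms of low to moderate incidence with no true difference. It also bars terms observed in under 5% of both arms, whatever their imbalance. Plotted estimates are exaggerated even where coverage is close to nominal, for example 7.7 points on average for a true 5 (25% v 20%).

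The sizes rest on the planned 275 per arm, on 5% meaning percentage points, and on assumed true rates. That no other between-arm interval exists for individual preferred terms is established only for the supplied text. No primary or key secondary conclusion is affected, and no adverse event goes unreported. It is a cheap improvement to make, not a threat to the trial's conclusions.

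**What to change.** Replace the difference-based rule in SAP 11.8.1 with one based on pooled incidence. Suggested content: plot every preferred term reported in at least 2% of subjects with both arms combined (11 of 550 at the planned size), plus all injection-site and hypersensitivity terms at any frequency, ordered by risk difference, with 90% CIs. The 2% is illustrative. The cut-off is the sponsor's choice and should be fixed before unblinding.

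For sparse terms, use a score or exact interval instead of Wald, because an arm with no events contributes zero to the Wald variance. The Protocol synopsis already describes exact limits based on the score statistic for two secondary immunogenicity proportions.

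The cost is a short SAP edit, a matching shell change and a longer figure. No new data are needed.
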